# 10.3 Appendix 3: Adverse Events: Definitions and Procedures for Recording, Evaluating, Follow-up, and Reporting

#### 10.3.1 Definitions of Medication Error, Misuse, and Abuse

#### **Medication error**

This is an unintended failure in the drug treatment process that leads to or has the potential to lead to harm to the patient.

#### Misuse

This refers to situations where the medicinal product is intentionally and inappropriately used not in accordance with the terms of the product information.

#### **Abuse**

This corresponds to the persistent or sporadic intentional, excessive use of a medicinal product for a perceived psychological or physiological reward or desired nontherapeutic effect.

#### **10.3.2 Definition of AE**

#### **AE** definition

- An AE is any untoward medical occurrence in a clinical study participant, temporally associated with the use of study intervention, whether or not considered related to the study intervention.
- Note: An AE can therefore be any unfavorable and unintended sign (including an abnormal laboratory finding), symptom, or disease (new or exacerbated) temporally associated with the use of a study intervention.
- Note: For purposes of AE definition, study intervention includes any pharmaceutical product, biological product, vaccine, diagnostic agent, medical device, combination product, or protocol-specified procedure whether investigational or marketed (including placebo, active comparator product, or run-in intervention), manufactured by, licensed by, provided by, or distributed by the Sponsor for human use in this study.

#### **Events meeting the AE definition**

- Any abnormal laboratory test results (hematology, clinical chemistry, or urinalysis) or other safety assessments (eg, ECG, radiological scans, vital signs measurements), including those that worsen from baseline, considered clinically significant in the medical and scientific judgment of the investigator.
- Exacerbation of a chronic or intermittent preexisting condition including either an increase in frequency and/or intensity of the condition.

PRODUCT: MK-2060 PROTOCOL/AMENDMENT NO.: 011-01

- New conditions detected or diagnosed after study intervention administration even though it may have been present before the start of the study.
- Signs, symptoms, or the clinical sequelae of a suspected drug-drug interaction.
- Signs, symptoms, or the clinical sequelae of a suspected overdose of either study intervention or a concomitant medication.
- For all reports of overdose (whether accidental or intentional) with an associated AE, the AE term should reflect the clinical symptoms or abnormal test result. An overdose without any associated clinical symptoms or abnormal laboratory results is reported using the terminology "accidental or intentional overdose without adverse effect."
- Any new cancer or progression of existing cancer.

#### **Events NOT meeting the AE definition**

- Medical or surgical procedure (eg, endoscopy, appendectomy): the condition that leads to the procedure is the AE.
- Situations in which an untoward medical occurrence did not occur (social and/or convenience admission to a hospital).
- Anticipated day-to-day fluctuations of preexisting disease(s) or condition(s) present or detected at the start of the study that do not worsen.
- Surgical procedure(s) planned prior to informed consent to treat a preexisting condition that has not worsened.
- Refer to Section 8.4.6 for protocol-specific exceptions.

#### **10.3.3 Definition of SAE**

If an event is not an AE per definition above, then it cannot be an SAE even if serious conditions are met.

### An SAE is defined as any untoward medical occurrence that, at any dose:

- a. Results in death
- b. Is life-threatening
  - The term "life-threatening" in the definition of "serious" refers to an event in which the participant was at risk of death at the time of the event. It does not refer to an event, which hypothetically might have caused death, if it were more severe.

PRODUCT: MK-2060 PROTOCOL/AMENDMENT NO.: 011-01

- c. Requires inpatient hospitalization or prolongation of existing hospitalization
  - Hospitalization is defined as an inpatient admission, regardless of length of stay, even if the hospitalization is a precautionary measure for continued observation. (Note: Hospitalization for an elective procedure to treat a preexisting condition that has not worsened is not an SAE.) A preexisting condition is a clinical condition that is diagnosed prior to the use of an MSD product and is documented in the participant's medical history.
- d. Results in persistent or significant disability/incapacity
  - The term disability means a substantial disruption of a person's ability to conduct normal life functions.
  - This definition is not intended to include experiences of relatively minor medical significance such as uncomplicated headache, nausea, vomiting, diarrhea, influenza, and accidental trauma (eg, sprained ankle) that may interfere with or prevent everyday life functions but do not constitute a substantial disruption.
- e. Is a congenital anomaly/birth defect
  - In offspring of participant taking the product regardless of time to diagnosis.
- f. Other important medical events
  - Medical or scientific judgment should be exercised in deciding whether SAE reporting is appropriate in other situations such as important medical events that may not be immediately life-threatening or result in death or hospitalization but may jeopardize the participant or may require medical or surgical intervention to prevent 1 of the other outcomes listed in the above definition. These events should usually be considered serious.
  - Examples of such events include invasive or malignant cancers, intensive treatment in an emergency room or at home for allergic bronchospasm, blood dyscrasias, or convulsions that do not result in hospitalization, or development of drug dependency or drug abuse.

#### 10.3.4 Additional Events Reported

#### Additional events that require reporting

In addition to the above criteria, AEs meeting either of the below criteria, although not serious per ICH definition, are reportable to the Sponsor.

- Is a cancer.
- Is associated with an overdose.

## 10.3.5 Recording AE and SAE

# AE and SAE recording

- When an AE/SAE occurs, it is the responsibility of the investigator to review all documentation (eg, hospital progress notes, laboratory, and diagnostics reports) related to the event.
- The investigator will record all relevant AE/SAE information on the AE CRFs/worksheets at each examination.
- It is not acceptable for the investigator to send photocopies of the participant's medical records to the Sponsor in lieu of completion of the AE CRF page.
- There may be instances when copies of medical records for certain cases are requested by the Sponsor. In this case, all participant identifiers, with the exception of the participant number, will be blinded on the copies of the medical records before submission to the Sponsor.
- The investigator will attempt to establish a diagnosis of the event based on signs, symptoms, and/or other clinical information. In such cases, the diagnosis (not the individual signs/symptoms) will be documented as the AE/SAE.

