#### 4.2.1 **Rationale for Endpoints**

#### 4.2.1.1 **Safety Endpoints**

Based on the data from P001 (healthy participant study), P004 (ESKD on HD study), P008 (ESKD on HD coadministered with Clopidogrel), and P007 (ongoing Phase 2 study in ESKD on HD with AVG) along with preclinical safety data, it is expected that single dose SC administration of MK-2060 will be well-tolerated in participants with CKD and ESKD. Physical examinations, VS, ECGs, laboratory safety tests (serum chemistry and hematology), aPTT, PT, and AEs related to bleeding will be assessed throughout the treatment period. AEs, including local infusion site reactions and systemic reactions to MK-2060 infusion, will be assessed throughout the treatment period.

08V5WO

Bleeding related AEs will include any sign or symptom of bleeding, even if not requiring intervention by a medical/healthcare professional, as well as clinically relevant nonmajor bleeding or major bleeding. As with all biologic medications, MK-2060 carries a risk of acute reactions upon exposure. These reactions can be categorized as common injection reactions, hypersensitivity reactions, and high cytokine release reactions. Acute reactions are usually mild, can occur even with the first dose, and can manifest with rigors, back pain, abdominal pain, nausea, vomiting, diarrhea, dyspnea, flushing, pruritus, and changes in heart rate or blood pressure. Acute hypersensitivity reactions typically occur after repeated exposures but can occur with the first dose. In addition to signs similar to common infusion reactions, participants may develop urticaria, wheezing, coughing, facial swelling, angioedema and more significant changes in VS. Cytokine release reactions are exceedingly rare but severe. They manifest as severe headache, nausea, vomiting, back pain, fever, hypotension and multiorgan failure. The risk of any of these reactions to MK-2060 is considered low given its profile in preclinical safety studies. There were no infusion reactions, no acute hypersensitivity reactions, and no cytokine release reactions observed thus far in any MK-2060 clinical studies. See the IB for more information on the Phase 1 clinical study experience with MK-2060.

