## 6.6.1 Stopping Rules

The following stopping rules will be used during the conduct of this study.

If any of the below stopping rules are met, the study will be paused, and no further dosing will occur until the Sponsor has reviewed the totality of data available. To continue the study (on joint agreement with the Sponsor and investigator), a substantial amendment will be submitted for approval.

- 1. An individual participant reports an SAE considered related to the study intervention by the investigator.
- 2. Two (2) or more participants within a Panel (at the same dose level) report Severe Nonserious AEs considered related to the study intervention by the investigator.
- 3. An increase in local lab aPTT >4.0-fold versus screening baseline as confirmed after repeat measurement in 2 or more participants in a panel. Local lab aPTT measured at Screening Visit should be used as baseline value.
- 4. An increase in local lab PT >1.5-fold versus screening baseline as confirmed after repeat measurement in 2 or more participants in a panel. Local lab PT measured at Screening Visit should be used as baseline value.

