#### **8.4.7** Events of Clinical Interest

Selected serious and nonserious AEs are also known as ECIs and must be reported to the Sponsor.

Events of clinical interest for this study include:

- 1. An overdose of Sponsor's product, as defined in Section 8.5.
- 2. Potential DILI events defined as an elevated AST or ALT laboratory value that is greater than or equal to 3× the ULN and an elevated total bilirubin laboratory value that is greater than or equal to 2× the ULN and, at the same time, an alkaline phosphatase laboratory value that is less than 2× the ULN, as determined by way of protocol-specified laboratory testing or unscheduled laboratory testing.\*
  - \*Note: These criteria are based on available regulatory guidance documents. The purpose of the criteria is to specify a threshold of abnormal hepatic tests that may require an additional evaluation for an underlying etiology. The study-site guidance for assessment and follow-up of these criteria can be found in the Investigator Study File Binder (or equivalent).

It may also be appropriate to conduct additional evaluation for an underlying etiology in the setting of abnormalities of liver blood tests including AST, ALT, bilirubin, and alkaline phosphatase that do not meet the criteria noted above. In these cases, the decision to proceed with additional evaluation will be made through consultation between the study investigators and the Sponsor Clinical Director. However, abnormalities of liver blood tests that do not meet the criteria noted above are not ECIs for this study.

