#### 9.4 Analysis Endpoints

#### **Primary Endpoints**

- 1. Primary endpoints are bleeding related AEs, AEs, and discontinuations due to AEs.
- Pharmacokinetics: The pharmacokinetic variables of primary interest for MK-2060 are measurement of MK-2060 plasma AUC0-∞, AUC0-168, Cmax, C168, Tmax, terminal t1/2, CL/F and Vz/F

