#### 9.6 Statistical Methods

Summary statistics and plots will be generated for raw laboratory safety tests, ECGs, and/or VS as well as for change from baseline, as deemed clinically appropriate. For all endpoints descriptive summary will be provided. For categorical measurements, counts and percentage numbers will be provided. Similarly, for continuous measurements, mean, standard deviation, median, min, max will be provided. Depending on the safety parameter, the difference from baseline will either be computed on the original scale (raw change from baseline) or on the log scale and back-transformed for reporting (percent change from baseline) as appropriate. Values will be listed for each PK parameter (including Tmax and apparent terminal t1/2), and appropriate non-model based descriptive statistics will be provided: N (number of participants with non-missing data), arithmetic mean, standard deviation, arithmetic percent CV (calculated as 100\*sqrt(exp(s2)-1), where s2 is the observed variance on the natural log-scale.)

PRODUCT: MK-2060 PROTOCOL/AMENDMENT NO.: 011-01

Descriptive statistics as well as appropriate plots will be displayed for aPTT fold change from baseline. Similar statistics will be provided for the fold changes in the exploratory endpoints such as PT and FXI activity levels.

To test the part 1 primary hypothesis, the posterior probability that the true geometric mean of AUC0-∞ after a single well-tolerated dose of MK-2060 in adult participants with CKD4 is at least 11345 nM\*hr, will be calculated using a noninformative prior. The CV for AUC0-∞ is expected to be approximately 30% (assuming similar variability as in MK-2060 P004). If this posterior probability exceeds 60%, then the primary research hypothesis will be supported.

Since Part 2 and Part 3 involves estimation, descriptive statistics (mean, median, standard deviation, min, max values) will be provided for primary and secondary endpoints.

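### The AE recording rule replaces signs with the diagnosis and makes no exception for bleeding, so a bleeding sign can be missed from the primary count of bleeding related AEs

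*Combined protocol and SAP*

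**What the plan says.** Section 9.4 lists the primary safety endpoints: "Primary endpoints are bleeding related AEs, AEs, and discontinuations due to AEs". Section 4.2.1.1 gives the first of these a broad scope: "Bleeding related AEs will include any sign or symptom of bleeding, even if not requiring intervention by a medical/healthcare professional". Clinically relevant nonmajor bleeding and major bleeding are included as well.

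Section 10.3.5 governs what is entered as the AE. It begins: "The investigator will attempt to establish a diagnosis of the event based on signs, symptoms, and/or other clinical information". It continues: "In such cases, the diagnosis (not the individual signs/symptoms) will be documented as the AE/SAE". The same list also asks for supporting detail: "The investigator will record all relevant AE/SAE information on the AE CRFs/worksheets at each examination".

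On analysis, Section 9.6 says: "For categorical measurements, counts and percentage numbers will be provided". Neither Section 9.4 nor Section 9.6 gives a term list, a flag or a case-review rule for deciding which AEs are bleeding related. The events of clinical interest in Section 8.4.7 are overdose and potential drug-induced liver injury. Bleeding is not among them. The synopsis states that there is no clinical adjudication committee.

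**The concern.** The endpoint is defined by what was seen or reported, down to trivial bleeding. The recording rule works at the level of the diagnosis. When the diagnosis names the bleed, the two agree. When it does not, an investigator who follows Section 10.3.5 as written enters a term with no bleeding in it. Hematuria becomes urinary tract infection, and blood in the stool becomes hemorrhoids.

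This matters because MK-2060 is an anti-Factor XI antibody, and Section 2.1 describes these patients as already at raised risk of bleeding. Low-dose aspirin and clopidogrel are permitted (Section 6.5). Exclusion criterion 8 bars gastrointestinal bleeding, duodenal polyps and gastric ulcer in the last 5 years, and severe hemorrhoidal bleeding in the last 3 months. Participants with older or milder lesions can therefore enrol. At stake is whether the bleeding count reported for each small group is complete by the protocol's own definition.

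**Working it through.** The plan gives no bleeding rate, power or precision for this endpoint, so there is no figure of its own to reproduce. The check is a comparison of the texts, followed by an illustration of scale.

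**Following one event through the plan.** Take a participant with visible hematuria in whom a urinary tract infection is diagnosed.

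1. Under Section 4.2.1.1 the hematuria is a sign of bleeding, so the participant has a bleeding related AE.
2. Under Section 10.3.5 the AE entered is urinary tract infection, not hematuria.
3. In the Section 9.6 tables the event counts under all AEs. Whether it also counts under bleeding related AEs is not stated.

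The event is missed from the bleeding count if both of these hold: the diagnosis entered does not name bleeding, and bleeding related AEs are selected by the recorded term. Section 10.3.5 can produce the first condition. The plan is silent on the second.

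**Scale of one or two events.** Inputs: 9 active participants per part (Sections 4.1 and 6.3.1). The number of bleeds recorded only under a diagnosis is an assumption. Exact (Clopper-Pearson) two-sided 95% intervals:

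| Bleeds counted | Rate | 95% interval |
|---|---|---|
| 0/9 | 0% | 0% to 33.6% |
| 1/9 | 11.1% | 0.3% to 48.2% |
| 2/9 | 22.2% | 2.8% to 60.0% |

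**Chance of seeing any bleeding AE in one active group.** Let p be the true proportion of participants with a bleed and m the share of those recorded under a non-bleeding diagnosis. Neither is in the documents; the ranges below are assumptions. The chance of at least one counted event is 1 − (1 − p(1 − m))^9, and the expected count is 9p(1 − m).

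For p = 20% and m = 25%: p(1 − m) = 0.15, the chance is 1 − 0.85^9 = 76.8%, and the expected count is 9 × 0.15 = 1.35. With m = 0 these are 1 − 0.80^9 = 86.6% and 1.80.

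| p | m = 0 | m = 10% | m = 25% | m = 50% |
|---|---|---|---|---|
| 10% | 61.3% | 57.2% | 50.4% | 37.0% |
| 20% | 86.6% | 83.2% | 76.8% | 61.3% |
| 30% | 96.0% | 94.1% | 89.9% | 76.8% |

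**The case against.** The strongest reply is that nothing in the plan says such events are excluded. Section 10.3.5 asks for a diagnosis of the event, and for a bleed that diagnosis may itself be a bleeding term. Section 4.2.1.1 defines bleeding by clinical content and is the trial-specific text, whereas Section 10.3.5 is generic. The earlier study MK-2060-004 reported hematuria and arteriovenous fistula hemorrhage as AEs, so bleeding signs have been reported as such in this programme. This all stands. It is why the point is that events can be missed, not that they necessarily drop out.

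A reader might also infer that missed events are beyond recovery. The documents do not support that. Section 10.3.5 wants all relevant information on the AE form and lets the sponsor request medical records. Hemoccult tests, hematology and physical examinations are scheduled in every part, and urinalysis in Parts 1 and 2. Part 3 has no scheduled urinalysis, however, and no section links any of these results to the bleeding endpoint. Recovery is possible but not prespecified. The CRF and data entry guidelines are not in the documents, so a bleeding field may already exist. If it does, the plan should refer to it.

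A third inference is that the stopping rules in Section 6.6.1 are weakened, because the first reads: "An individual participant reports an SAE considered related to the study intervention by the investigator". That is speculative. The causality guidance in Section 10.3.5 asks about other causes whichever term is entered, so hematuria recorded on its own could equally be attributed to infection. The aPTT and PT rules do not use AE terms at all.

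Finally, the recording rule applies alike to placebo under the blind in Parts 1 and 2, and safety is summarized descriptively with no test. Equal application does not restore a missed bleed to the active group's count, and Part 3 has no placebo group.

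**Conclusion.** The point holds as a gap between two rules of the protocol. Bleeding related AEs are defined by signs and symptoms, the AE record is kept by diagnosis, and nothing reconciles the two. A bleeding sign attributed to a diagnosis that does not name bleeding can be missed from one of the three primary safety components. It stays in the all-AE component, and it may be partly recoverable from other data.

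The size of the loss cannot be determined from the documents. The change from 1/9 to 0/9, and the fall from 86.6% to 76.8% at an assumed 20% bleeding rate with 25% of bleeds recorded under a non-bleeding diagnosis, only illustrate how sensitive groups of 9 are. They are not estimates of what will happen. The documents do not support saying that the primary safety count as a whole is lowered, that bleeds are certain to be lost, or that the stopping rules are impaired. What remains is enough to justify a short amendment, because the ambiguity sits in a primary safety endpoint of an anticoagulant antibody and is cheap to remove.

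**What to change.** Add one sentence to Section 10.3.5: any sign or symptom of bleeding is recorded as its own AE, in addition to any underlying diagnosis, and the diagnosis does not replace it. Marking the AE as bleeding, yes or no, on the AE form would serve as an alternative.

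Add one sentence to Section 9.4: the bleeding endpoint is the number of participants with at least one AE so recorded or flagged, each counted once per part. Counting per part matters because Section 4.1 allows participants who complete Part 1 to enter Part 2.

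Bring the AE entry guidelines into line with both sentences. The cost is two sentences and a guideline update, or one extra field if the flag is chosen. Separate recording gives some episodes two AE rows. Counting participants instead of rows keeps the bleeding endpoint from being inflated. The change concerns recording and counting only and leaves dosing and clinical management as they are.

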## Assessment of intensity/toxicity

- An event is defined as "serious" when it meets at least 1 of the predefined outcomes as described in the definition of an SAE, not when it is rated as severe.
- The investigator will make an assessment of intensity for each AE and SAE (and other reportable safety event) reported during the study and assign it to 1 of the following categories:
  - Mild: An event that is easily tolerated by the participant, causing minimal discomfort, and not interfering with everyday activities (for pediatric studies, awareness of symptoms, but easily tolerated).
  - Moderate: An event that causes sufficient discomfort to interfere with normal everyday activities (for pediatric studies, definitely acting like something is wrong).
  - Severe: An event that prevents normal everyday activities. An AE that is assessed as severe should not be confused with an SAE. Severe is a category used for rating the intensity of an event; and both AE and SAE can be assessed as severe (for pediatric studies, extremely distressed or unable to do usual activities).

